4.4 Early study termination

The study can be terminated at any time for any reason by Novartis. Should this be necessary, the patient should be seen as soon as possible and the assessments described in [Section 7](#) for a discontinued or withdrawn patient should be performed. The investigator may be informed of additional procedures to be followed in order to ensure that adequate consideration is given to the protection of the patient's interests. The investigator will be responsible for informing IRBs and/or ECs of the early termination of the trial.

5 Population

5.1 Patient population

The study will include men and postmenopausal women with HR+, HER2-negative advanced (loco regionally recurrent not amenable to curative therapy or metastatic) breast cancer which progressed on or after AI treatment.

Patients with symptomatic visceral disease or any disease burden that makes the patient ineligible for endocrine therapy per the investigator's best judgment will not be included in this study.

The investigator or designee must ensure that only patients who meet all the following inclusion and none of the exclusion criteria are offered treatment in the study.

The patients are not permitted to participate in additional parallel investigational drug or device studies.

5.2 Inclusion criteria

Patients eligible for inclusion in this study have to meet **all** of the following criteria:

Written informed consent must be obtained prior to any screening procedures

1. Patient is an adult ≥ 18 years old at the time of informed consent and has signed informed consent before any trial related activities and according to local guidelines.
2. Patient has adequate tumor tissue for the analysis of *PIK3CA* mutational status by a Novartis designated laboratory. One new or recent biopsy (collected at screening if feasible) or archival tumor block or slides (15 slides minimum from a surgical specimen, 20 slides minimum from a biopsy) must be provided. It is recommended to provide a tumor sample collected after the most recent progression or recurrence.
3. Patient has identified *PIK3CA* status (mutant or non-mutant; determined by a Novartis designated laboratory).
4. If female, then the patient is postmenopausal. Postmenopausal status is defined either by:
 - Prior bilateral oophorectomy

- Age ≥ 60
- Age <60 and amenorrheic for 12 or more months in the absence of chemotherapy, tamoxifen, toremifene, or ovarian suppression and Follicle-stimulating Hormone (FSH) and estradiol in the postmenopausal range per local normal range

Note: For women with therapy-induced amenorrhea, serial measurements of FSH and/or estradiol are needed to ensure postmenopausal status ([NCCN.2.2015](#)). Ovarian radiation or treatment with a luteinizing hormone-releasing hormone agonist (LH-RHa) (goserelin acetate or leuprolide acetate) is not permitted for induction of ovarian suppression in this trial.

5. Patient has radiological or objective evidence of recurrence or progression.
6. Patient has a histologically and/or cytologically confirmed diagnosis of ER+ and/or PgR+ breast cancer by local laboratory.
7. Patient has HER2-negative breast cancer defined as a negative in situ hybridization test or an IHC status of 0, 1+ or 2+. If IHC is 2+, a negative in situ hybridization (FISH, CISH, or SISH) test is required by local laboratory testing.
8. Patient has either:
 - Measurable disease, i.e., at least one measurable lesion as per RECIST 1.1 criteria (a lesion at a previously irradiated site may only be counted as a target lesion if there is clear sign of progression since the irradiation) OR
 - If no measurable disease is present, then at least one predominantly lytic bone lesion must be present (patients with no measurable disease and only one predominantly lytic bone lesion that has been previously irradiated are eligible if there is documented evidence of disease progression of the bone lesion after irradiation).
9. Patient has advanced (loco regionally recurrent not amenable to curative therapy or metastatic) breast cancer.
Patients may be:
 - relapsed with documented evidence of progression while on (neo) adjuvant endocrine therapy or within 12 months from completion of (neo)adjuvant endocrine therapy with no treatment for metastatic disease
 - relapsed with documented evidence of progression more than 12 months from completion of (neo)adjuvant endocrine therapy and then subsequently progressed with documented evidence of progression while on or after only one line of endocrine therapy for metastatic disease
 - newly diagnosed advanced breast cancer, then relapsed with documented evidence of progression while on or after only one line of endocrine therapy

Note: i) Patients with newly diagnosed endocrine treatment naïve advanced breast cancer, ii) ii) Patient who relapsed with documented evidence of progression on/or within 12 months from completion of adjuvant endocrine therapy and then subsequently relapsed with documented evidence of progression after one line of endocrine therapy (with either an antiestrogen or an AI) for metastatic disease will NOT be included in the study.

10. Patient has recurrence or progression of disease during or after AI therapy (i.e. letrozole, anastrozole, exemestane). AI therapy does not need to be the latest treatment regimen.
11. Patient has an ECOG performance status 0 or 1

12. Patient has adequate bone marrow and organ function as defined by the following laboratory values (as assessed by central laboratory for eligibility):

- Absolute neutrophil count $\geq 1.5 \times 10^9/L$
- Platelets $\geq 100 \times 10^9/L$
- Hemoglobin $\geq 9.0 \text{ g/dL}$
- Calcium (corrected for serum albumin) and magnesium within normal limits or \leq grade 1 according to NCI-CTCAE version 4.03 if judged clinically not significant by the investigator
- Potassium within normal limits, or corrected with supplements
- International Noramlized Ratio (INR) ≤ 1.5
- Creatinine Clearance $\geq 35 \text{ mL/min}$ using Cockcroft-Gault formula
- In absence of liver metastases, ALT and AST $\leq 2.5 \times \text{ULN}$. If the patient has liver metastases, ALT and AST $\leq 5 \times \text{ULN}$
- Total bilirubin $< \text{ULN}$ except for patients with Gilbert's syndrome who may only be included if the total bilirubin is $\leq 3.0 \times \text{ULN}$ or direct bilirubin $\leq 1.5 \times \text{ULN}$
- Fasting plasma glucose (FPG) $\leq 140 \text{ mg/dL}$ (7.7 mmol/L)* and Glycosylated Hemoglobin (HbA1c) $\leq 6.4\%$ (both criteria have to be met)
- Fasting Serum amylase $\leq 2 \times \text{ULN}$
- Fasting Serum lipase $\leq \text{ULN}$

*For patients with FPG $\geq 100 \text{ mg/dL}$ and/or HbA1c $\geq 5.7\%$ (i.e. threshold for pre-diabetes) at screening, -recommend lifestyle changes according to ADA guidelines, i.e. dietary advice (e.g. small frequent meals, low carbohydrate content, high fiber, balancing carbohydrate intake over the course of the day, three small meals and 2 small snacks rather than one large meal) and exercise. A consultation with a diabetologist is highly recommended.

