6.3.1.2 Alpelisib/placebo

Management of severe or intolerable adverse reactions requires dose reduction, temporary interruption, and/or discontinuation of alpelisib therapy. A maximum of 2 dose reductions will be allowed, after which the patient will be discontinued from treatment with alpelisib/placebo. Dose reduction should be based on the worst preceding toxicity.

Please refer to [Table 6-2](#) and [Table 6-3](#) for guidance.

Table 6-2 Dose reduction sequential steps for alpelisib/placebo

Alpelisib/placebo dose level	Dose and schedule	Number of tablets & strength
Starting dose	300 mg/day continuously	1 x 200 mg tablet and 2 x 50 mg tablet
Dose level -1	250 mg/day continuously	1 x 200 mg tablet and 1 x 50 mg tablet
Dose level -2	200 mg/day continuously	1 x 200 mg tablet

Recommendations for dose reduction or dose interruption of alpelisib/placebo in the management of adverse reactions are summarized in [Table 6-3](#). No dose modification for fulvestrant is permitted. Clinical judgment of the treating physician, including confirmation of lab values if deemed necessary, should guide the management plan of each patient based on individual benefit/risk assessment.

However, treatment must be discontinued as indicated in [Table 6-3](#).

After treatment is resumed at a lower dose:

- If the same toxicity recurs with the same severity, then the next treatment re-initiation must resume at a lower dose irrespective of duration.
- Once the alpelisib/placebo dose has been reduced, no re-escalation will occur, even upon resolution of AE.

If a patient requires a dose delay of alpelisib/placebo for > 28 days from the intended day then the patient must be discontinued from alpelisib/placebo, but may continue on fulvestrant. All scheduled assessments will continue to be performed. If fulvestrant is held for more than 35 days since a planned injection, then fulvestrant should be permanently discontinued. The patient may continue on alpelisib/placebo at the discretion of the investigator until study completion, in which case all scheduled assessments will continue to be performed.

Table 6-3 Criteria for interruption and re-initiation of alpelisib/placebo treatment

Dose Modifications for alpelisib/placebo as specified below. Fulvestrant may be continued while alpelisib/placebo dose is being held, at the investigators discretion, and as specified in Section 6.3.1	
Worst toxicity -CTCAE Grade (value)	Dose Modifications for alpelisib/placebo

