Grade 1 (> ULN - $1.5 \times$ ULN)	No dose adjustment is required. Initiate appropriate medical therapy and monitor as clinically indicated.
Grade 2 (> $1.5 - 3.0 \times$ ULN)	Omit dose until resolved to \leq Grade 1, then: 
 • If resolved in \leq 14 days, then maintain dose level • If resolved in $>$ 14 days, then \downarrow 1 dose level
Grade 3 (> $3.0 - 10.0 \times$ ULN)*	Interrupt dose until recovery to Grade \leq 1, then resume at the next lower dose level.
Grade 4 (> $10.0 \times$ ULN)*	Permanently discontinue patient from alpelisib/placebo
Isolated AST or ALT Elevation	
Grade 1 (> ULN – $3.0 \times$ ULN)	Maintain dose level. Initiate appropriate medical therapy and monitor as clinically indicated.
Grade 2 (> $3.0 - 5.0 \times$ ULN)	No dose adjustment is required. Initiate appropriate medical therapy and monitor as clinically indicated.

Dose Modifications for alpelisib/placebo as specified below. Fulvestrant may be continued while alpelisib/placebo dose is being held, at the investigators discretion, and as specified in Section 6.3.1	
Worst toxicity -CTCAE Grade (value)	Dose Modifications for alpelisib/placebo
Grade 3 (> 5.0 - 20.0 x ULN) •	Interrupt dose until recovery to Grade ≤ 1, then resume at the next lower dose level. •
Grade 4 (> 20.0 x ULN) •	Permanently discontinue.
Combined ^a elevations of AST or ALT and total Bilirubin	Please see specific instructions in Section 6.3.2.1.5
	•
All dose modifications should be based on the worst preceding toxicity.	
^a "Combined" defined as total bilirubin increase to the defined threshold concurrently with ALT/AST increase to the defined threshold	
If combined elevations of AST or ALT and total bilirubin do not meet the defined thresholds, please follow the instructions for isolated elevation of total bilirubin and isolated elevation of AST/ALT, and take a conservative action based on the degree of the elevations (e.g. discontinue treatment at the situation when omit dose is needed for one parameter and discontinue treatment is required for another parameter). After all elevations resolve to the defined thresholds that allow treatment re-initiation, re-start the treatment either at the same dose or at one dose lower if meeting a criterion for dose reduction	

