* Note: If total bilirubin > 3.0 x ULN is due to the indirect (non-conjugated) component only, and hemolysis as the etiology has been ruled out as per institutional guidelines (e.g. review of peripheral blood smear and haptoglobin determination), then ↓ 1 dose level and continue treatment at the discretion of the investigator.	

Dose Modifications for alpelisib/placebo as specified below. Fulvestrant may be continued while alpelisib/placebo dose is being held, at the investigators discretion, and as specified in Section 6.3.1	
Worst toxicity -CTCAE Grade (value)	Dose Modifications for alpelisib/placebo
Investigations (Cardiac)	
Cardiac – QTc prolongation	
QTcF > 500 ms (\geq Grade 3) or > 60 ms change from baseline on at least two separate ECGs	
First Occurrence:
 
 1. Assess the quality of the ECG recording and the QT value and repeat if needed 2. Interrupt study treatment 3. Determine the serum electrolyte levels (in particular hypokalemia, hypomagnesemia). If abnormal, correct abnormalities before resuming study drug treatment. 4. Review concomitant medication use for other causes for QT prolongation (refer to crediblemeds.org for known QT prolonging drugs), and for drugs with the potential to increase the risk of drug exposure related QT prolongation 5. Check study drug dosing schedule and treatment compliance 6. Consider collecting a time-matched PK sample and record time and date of last study drug intake. 
After confirming ECG reading at site, if QTcF > 500 ms or > 60 ms change from baseline
 
 • Interrupt study treatment • Repeat ECG and confirm ECG diagnosis by a cardiologist 
If QTcF confirmed > 500 ms or > 60 ms change from baseline
 
 • Correct electrolytes, eliminate culprit concomitant treatments, and identify clinical conditions that could potentially prolong the QT • Consult with a cardiologist (or qualified specialist) • Increase cardiac monitoring as indicated, until the QTcF returns to \leq 480 ms or < 60ms change from baseline. • After resolution to \leq 480 ms /60 ms change from baseline, consider re-introducing treatment at reduced dose, and increase ECG monitoring • If QTcF remains \leq 500 ms/60 ms change from baseline after dose reduction, continue planned ECG monitoring during subsequent treatment • If QTcF recurs > 500 ms/60 ms change from baseline after dose reduction, discontinue patient from alpelisib/placebo.

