14.7 Appendix 7: Liver event and Laboratory trigger Definitions and Follow-up Requirements

Table 14-13 Liver event and laboratory trigger definitions

	Definition/threshold
LIVER LABORATORY TRIGGERS	3 x ULN < ALT / AST \leq 5 x ULN · 1.5 x ULN < TBL \leq 2 x ULN
LIVER EVENTS	ALT or AST $>$ 5 x ULN
	ALP $>$ 2 x ULN (in the absence of known bone pathology)

Definition/threshold
TBL > 2 × ULN (in the absence of known Gilbert syndrome)
ALT or AST > 3 × ULN and INR > 1.5
Potential Hy's Law cases (defined as ALT or AST > 3 × ULN and TBL > 2 × ULN [mainly conjugated fraction] without notable increase in ALP to > 2 × ULN)
Any clinical event of jaundice (or equivalent term)
ALT or AST > 3 × ULN accompanied by (general) malaise, fatigue, abdominal pain, nausea, or vomiting, or rash with eosinophilia
Any adverse event potentially indicative of a liver toxicity*

*These events cover the following: Hepatic failure, fibrosis and cirrhosis, and other liver damage-related conditions; the non-infectious hepatitis; the benign, malignant and unspecified liver neoplasms TBL: total bilirubin; ULN: upper limit of normal

Based on investigator's discretion investigation(s) for contributing factors for the liver event can include: Serology tests, imaging and pathology assessments, hepatologist's consultancy; obtaining more detailed history of symptoms and prior or concurrent diseases, history of concomitant drug use, exclusion of underlying liver disease

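### Criterion 12 admits patients with Gilbert's syndrome at bilirubin values for which the Grade 2 row of Table 6-3 withholds alpelisib/placebo, with no provision for an elevated entry value

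*Protocol*

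**What the plan says.** **Entry (Protocol 5.2, criterion 12).** Total bilirubin must be below ULN "except for patients with Gilbert's syndrome who may only be included if the total bilirubin is" at most 3.0 x ULN, or direct bilirubin is at most 1.5 x ULN. ALT and AST may be up to 2.5 x ULN, or up to 5 x ULN with liver metastases.

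**Isolated bilirubin (Table 6-3, Section 6.3.1.2).** Grade 1 runs from ULN to 1.5 x ULN and needs no dose change. At Grade 2, above 1.5 and up to 3.0 x ULN, the instruction is "Omit dose until resolved to" Grade 1 or better. The dose level is then kept if this took 14 days or less, and lowered by one level otherwise. An asterisked note, attached to the Grade 3 and 4 rows, covers a total above 3.0 x ULN that "is due to the indirect (non-conjugated) component only, and hemolysis as the etiology has been ruled out". In that case the dose drops one level and treatment may continue at the investigator's discretion.

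**Isolated AST/ALT (Table 6-3).** Above 3.0 and up to 5.0 x ULN needs no dose adjustment. Above 5.0 and up to 20.0 x ULN means interruption until Grade 1 or better (3.0 x ULN or lower), then restart one level lower.

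**Long holds (Section 6.3.1.2).** For a delay of more than 28 days the rule is: "from the intended day then the patient must be discontinued from alpelisib/placebo". Section 7.1.3 repeats this limit.

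**The concern.** The eligibility criteria make a deliberate exception for Gilbert's syndrome, but the isolated-bilirubin rows contain no matching provision. For part of the admitted group, the dosing table responds to the value the patient brought into the trial. If a site follows the row, such a patient can lose alpelisib/placebo although nothing has changed on treatment. If another site uses its judgment, it will act differently on the same value.

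The reporting is affected too. Protocol 8.1.2.1 treats a laboratory abnormality that leads to a protocol-required dose hold as an adverse event by definition. Protocol 10.5.3.6 and SAP 3.6.4 summarize interruptions, reductions and discontinuations with their reasons. An unchanged entry value could therefore appear in either arm as hepatic intolerance.

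**Working it through.** There is no sample size, power or alpha figure to reproduce. The check sets the entry limits against the Table 6-3 limits, all in multiples of ULN.

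| | Highest entry value | Dose withheld | Restart allowed |
|---|---|---|---|
| Total bilirubin, Gilbert's syndrome | 3.0 (or direct at most 1.5) | above 1.5 | 1.5 or lower |
| ALT/AST, liver metastases | 5.0 | above 5.0 | 3.0 or lower |
| ALT/AST, no liver metastases | 2.5 | above 5.0 | 3.0 or lower |

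**Bilirubin.**
1. The part of the Gilbert's entry range above 1.5 and up to 3.0 is exactly the Grade 2 omission band. A patient entering at 2.0 meets the omission rule at the first on-treatment bilirubin with no change in value.
2. The fall needed to restart is (entry - 1.5) / entry. From 2.0 this is 0.5 / 2.0 = 25%. From 3.0 it is 1.5 / 3.0 = 50%.
3. If the value stays in the band, the hold passes 28 days and the discontinuation rule applies.
4. Gilbert's patients who enter at 1.5 or lower are not affected.
5. For purely indirect bilirubin with hemolysis excluded, a value of 2.0 means the drug is withheld. A value of 4.0 means one dose level lower with treatment continuing at discretion. The instruction to stop dosing therefore applies at the lower value and can be avoided at the higher one.
6. The direct-bilirubin alternative can be read as admitting a total above 3.0. Such a patient would start in the Grade 3 or Grade 4 band, or under the note, so the entry value again prompts an action.

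**ALT/AST.**
1. Entry above 3.0 and up to 5.0 is Grade 2 in the table, and no dose change follows. The entry value alone triggers nothing.
2. After a rise above 5.0, restart needs 3.0 or lower. The fall below entry is (entry - 3.0) / entry. From 4.0 this is 1.0 / 4.0 = 25%. From 5.0 it is 2.0 / 5.0 = 40%. A return to baseline does not permit restart.
3. Patients without liver metastases enter at 2.5 or lower, which is below the restart limit, so there is no conflict.

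**How the protocol treats elevated entry values elsewhere.**
- The Grade 1 glucose row of Table 6-3 is limited to values above 140 mg/dL for patients who enter between ULN and 140 mg/dL.
- The amylase/lipase row sets recovery at the patient's baseline.
- Section 6.3.2.1.5 on combined liver elevations has separate criteria for patients with elevated baseline values.
- Table 14-13 (Appendix 7) counts a total bilirubin above 2 x ULN as a liver event only "in the absence of known Gilbert syndrome".

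The isolated bilirubin and AST/ALT rows have no equivalent.

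**The case against.** **Clinical judgment governs.** Section 6.3.1.2 calls the omission and reduction rows recommendations for managing adverse reactions and leaves each patient's plan to the physician. A stable entry value is arguably not an adverse reaction, since Section 8.1.1 defines an adverse event by appearance or worsening. This softens the conflict. It does not remove it, because the rows are keyed to values in multiples of ULN, the 28-day rule is worded as mandatory, and judgment supplies no baseline reference.

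**The bilirubin might fall.** The documents say nothing about its course in Gilbert's syndrome. The discontinuation step is therefore conditional on the value staying in the band.

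**The inconsistency is not one-directional.** The note costs a dose level that cannot be regained, whereas the Grade 2 row keeps the dose if recovery takes 14 days or less. That is correct. The mismatch concerns whether dosing stops, not every consequence.

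**Appendix 7 is not a dosing rule.** Also correct. It shows only that Gilbert's syndrome was considered elsewhere.

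**Stronger readings that the documents do not support.** A reader might infer that the conflict diluted the primary PFS contrast. Enrollment closed on 21 July 2017, and Amendment 5 (February 2020) describes the primary endpoint as already met. The same amendment changed the AST/ALT/bilirubin dose modifications, so the current rows cannot be read back into the period behind the primary result. A reader might also infer that liver-metastasis patients breach the table at their entry value, and they do not. Applying an assumed prevalence of Gilbert's syndrome to the cohort would give no reliable count either, since it would include entrants at 1.5 x ULN or lower.

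**Conclusion.** The bilirubin conflict holds. For Gilbert's patients admitted above 1.5 and up to 3.0 x ULN, Table 6-3 read literally withholds alpelisib/placebo at an unchanged entry value and leads to discontinuation if the value persists beyond 28 days. The table is also inconsistent with itself for indirect bilirubin on either side of 3.0 x ULN.

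The ALT/AST point is secondary. It concerns only liver-metastasis patients who enter above 3.0 x ULN and later exceed 5.0 x ULN, and it lies in the restart limit. Requiring a low value after a new Grade 3 rise may be a deliberate safety choice, but the text does not say so for patients whose entry value was already higher.

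The size is unknown: the documents give no frequency for either group, and no effect on the hazard ratio, power or type I error is shown. This is a gap in the dosing instructions and in how interruptions would be recorded. It rests on reading the rows as printed, without an unwritten baseline exception.

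**What to change.** Reconcile criterion 12 in Section 5.2, the isolated bilirubin and AST/ALT rows of Table 6-3, the indirect-bilirubin note and the 28-day rule in Section 6.3.1.2. In doing so, take account of the glucose and amylase/lipase rows and Section 6.3.2.1.5, which already address elevated entry values, and of the Gilbert's exemption in Appendix 7. The result should tell a site plainly what applies to a patient whose entry value already lies in a band that calls for action, and whether return to the entry value permits restart.

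Changing criterion 12 would now affect no new patient, so the wording of Table 6-3 is the practical place. The sponsor must decide which limit governs; no threshold or dosing rule is proposed here. The cost is a text change in the next amendment, with no new assessments.
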